9 ASSESSMENT OF SAFETY

9.1 Specification of Safety Parameters

9.1.1 Unanticipated Problems

The Office for Human Research Protections (OHRP) considers unanticipated problems involving risks to subjects or others to include, in general, any incident, experience, or outcome that meets **all** of the following criteria:

- unexpected in terms of nature, severity, or frequency given (a) the research procedures that are described in the protocol-related documents, such as the IRB-approved research protocol and informed consent document; and (b) the characteristics of the subject population being studied;
- related or possibly related to participation in the research (“possibly related” means there is a reasonable possibility that the incident, experience, or outcome may have been caused by the procedures involved in the research); and
- suggests that the research places subjects or others at a greater risk of harm (including physical, psychological, economic, or social harm) than was previously known or recognized.

Per the definition, only a subset of adverse events would be characterized as unanticipated problems. There are other types of incidents, experiences, and outcomes that are not considered adverse events, but are characterized as unanticipated problems (e.g., breach of confidentiality or other incidents involving social or economic harm).

9.1.2 Adverse Events

An adverse event is any untoward or unfavorable medical occurrence in a human subject, including any abnormal sign (for example, abnormal physical exam or laboratory finding), symptom, or disease, temporally associated with the subject’s participation in the research, whether or not considered related to the subject’s participation in the research.

9.1.3 Serious Adverse Events

Serious adverse events (SAEs) are a subset of all adverse events

A serious adverse event (SAE) is one that meets one or more of the following criteria:

- Results in death
- Is life-threatening (places the subject at immediate risk of death from the event as it occurred)
- Results in inpatient hospitalization or prolongation of existing hospitalization
- Results in a persistent or significant disability or incapacity

- Results in a congenital anomaly or birth defect
- An important medical event that may not result in death, be life threatening, or require hospitalization may be considered an SAE when, based upon appropriate medical judgment, the event may jeopardize the subject and may require medical or surgical intervention to prevent one of the outcomes listed in this definition.

9.2 Time Period and Frequency for Event Assessment and Follow-Up

Unanticipated problems, AEs and SAEs will be recorded in the data collection system throughout the study.

Given the nature of the intervention (a referral letter and dental information guide), it is unlikely that intervention-related SAEs or AEs will occur. However, throughout the study, if a caregiver or teacher reports an event to any study staff; it will be communicated to the PI immediately. The PI will record all reportable events occurring any time after informed consent is obtained until the last day of study participation. Events will be followed for outcome information until resolution or stabilization.

9.3 Characteristics of an Adverse Event

9.3.1 Relationship to Study Intervention

To assess relationship of an event to study intervention, the following guidelines are used:

1. Related (Possible, Probable, Definite)
 - a. The event is known to occur with the study intervention.
 - b. There is a temporal relationship between the intervention and event onset.
 - c. The event abates when the intervention is discontinued.
 - d. The event reappears upon a re-challenge with the intervention.
2. Not Related (Unlikely, Not Related)
 - a. There is no temporal relationship between the intervention and event onset.
 - b. An alternate etiology has been established.

9.3.2 Expectedness of SAEs

Given the nature of the intervention (a referral letter), it is unlikely that SAEs or AEs will occur which are related to the intervention/study. The NIDCR Medical Monitor and the Study PI will be responsible for determining whether an SAE/AE is expected or unexpected. An adverse event will be considered unexpected if the nature, severity, or frequency of the event is not consistent with the risk information previously described for the intervention.

9.3.3 Severity of Event

The following scale will be used to grade adverse events:

1. Mild: no intervention required; no impact on activities of daily living (ADL)
2. Moderate: minimal, local, or non-invasive intervention indicated; moderate impact on ADL
3. Severe: significant symptoms requiring invasive intervention; subject seeks medical attention, needs major assistance with ADL

9.4 Reporting Procedures

9.4.1 Unanticipated Problem Reporting to IRBs and NIDCR

Incidents or events that meet the OHRP criteria for unanticipated problems require the creation and completion of an unanticipated problem report form. The following information will be included when reporting an adverse event, or any other incident, experience, or outcome as an unanticipated problem to the University Hospitals Case Medical Center (UHCMC) IRB:

- appropriate identifying information for the research protocol, such as the title, investigator's name, and the IRB project number;
- a detailed description of the adverse event, incident, experience, or outcome;
- an explanation of the basis for determining that the adverse event, incident, experience, or outcome represents an unanticipated problem;
- a description of any changes to the protocol or other corrective actions that have been taken or are proposed in response to the unanticipated problem.

To satisfy the requirement for prompt reporting, unanticipated problems will be reported using the following timeline:

- Unanticipated problems that are serious adverse events will be reported to the UHCMC IRB and to NIDCR (Medical Monitor and Program Official) within 1 week of the study staff/PI becoming aware of the event.
- Any other unanticipated problem will be reported to the UHCMC IRB and to NIDCR (Medical Monitor and Program Official) within 2 weeks of the study staff/PI becoming aware of the problem.

All unanticipated problems will be reported to NIDCR's centralized reporting system via Rho Product Safety:

- Product Safety Fax Line (US): [name]

- Product Safety Email: [contact]

General questions about SAE reporting will be directed to the Rho Product Safety Help Line (available 8:00AM – 5:00PM Eastern Time):

- US: [name]

9.4.2 Serious Adverse Event Reporting to NIDCR

Any AE meeting the specified Serious Adverse Event criteria will be submitted (by fax or email) on an SAE form to NIDCR's centralized safety system via Rho Product Safety. Once submitted, Rho Product Safety will send a confirmation email to the investigator within 1 business day. The investigator will contact Rho Product Safety if this confirmation is not received. This process applies to both initial and follow-up SAE reports.

SAE Reporting Contact Information:

- Product Safety Fax Line (US): [name]
- Product Safety Email: [contact]

General questions about SAE reporting will be directed to the Rho Product Safety Help Line (available 8:00AM – 5:00PM Eastern Time):

- US: [name]

The PI will complete a Serious Adverse Event Form and submit via fax or email within the following timelines:

- All deaths and immediately life-threatening events, whether related or unrelated, will be recorded on the Serious Adverse Event Form and submitted to Product Safety within 24 hours of site awareness.
- Serious adverse events other than death and immediately life-threatening events, regardless of relationship, will be reported by fax within 72 hours of site awareness.

All SAEs will be followed until resolution or stabilization.

9.5 Halting Rules

Discontinuation of the study will be determined by standard NIH policies and procedures. Given that the study procedures are deemed “minimal risk”, it is unlikely that the trial would need to be discontinued early because of concern for human subjects. The PI and NIDCR will share responsibility in monitoring progress on this study, including progress toward meeting the recruitment and retention goals, data quality and integrity, and protections of human subjects.

10 STUDY OVERSIGHT

In addition to the PI's responsibility for oversight, study oversight will be under the direction of the NIDCR Medical Monitor. The PI will submit a report every 6 months to the NIDCR Medical Monitor for review. This report will include data regarding enrollment and retention, unanticipated problems and protocol deviations, disposition of biospecimens, outcome measures, quality management findings and other relevant parameters. If necessary, additional steps may be taken to ensure data integrity and protocol compliance.

11 CLINICAL SITE MONITORING

Clinical site monitoring is conducted to ensure that the rights of human subjects are protected, that the study is implemented in accordance with the protocol and/or other operating procedures, and that the quality and integrity of study data and data collection methods are maintained. Monitoring for this study will be performed by NIDCR's Clinical Research Operations and Management Support (CROMS) contractor. The monitor will evaluate study processes and documentation based on NIDCR standards and the International Conference on Harmonisation (ICH), E6: Good Clinical Practice guidelines (GCP).

Details of clinical site monitoring will be documented in a Clinical Monitoring Plan (CMP) developed by the CROMS contractor, in collaboration with the NIDCR Office of Clinical Trials and Operations Management (OCTOM) and the NIDCR Program Official. The CMP will specify the frequency of monitoring, monitoring procedures, the level of clinical site monitoring activities (e.g., the percentage of subject data to be reviewed), and the distribution of monitoring reports. Some monitoring activities may be performed remotely, while others will take place at the study site(s). Staff from the CROMS contractor will conduct monitoring activities and provide reports of the findings and associated action items in accordance with the details described in the CMP. Documentation of monitoring activities and findings will be provided to the site study team, the study PIs, OCTOM, and the NIDCR. The NIDCR reserves the right to conduct independent audits as necessary.

12 STATISTICAL CONSIDERATIONS

12.1 Study Hypotheses

We hypothesize that the CSM-based interventions will increase receipt of dental care compared to the modified standard referral letter.

12.2 Sample Size Considerations

The primary aims are to compare dental care receipt among the five intervention groups, overall and separately for each study site (Ohio and Washington).

The five intervention groups are:

Arm 1: CSM referral letter alone (N=204)

Arm 2: CSM referral letter + DIG (N=204)

Arm 3: Reduced CSM referral letter alone (N=24)

Arm 4: Reduced CSM referral letter + DIG (N=24)

Arm 5: Modified Standard letter (N=204)

The utilization will be defined as evidence of dental care through restorations or extractions at the final study visit exam that was previously not found during the baseline exam. All changes will be recorded on a tooth level using ICDAS criteria and then dichotomized at the caregiver level as having obtained or not obtained dental care for their child/children.

There are three treatment comparisons to assess the overall CSM referral letter and DIG: CSM referral letter alone versus standard letter (Arm 1 vs Arm 5), CSM referral letter plus DIG versus standard letter (Arm 2 vs Arm 5), and CSM referral letter alone versus CSM referral letter plus DIG (Arm 1 vs Arm 2). As described below we address the issue of multiple testing, both multiple comparisons and multiple sites, using a gatekeeper approach. By specifying a sequence of tests, this approach will allow for the use of a nominal 0.05 alpha level for each test while maintaining a 0.05 family-wise alpha level for the six tests (three at each study site).

An additional comparison will be conducted to assess the effect of the targeted component (e.g., the ‘timeline’ text): CSM referral letter with and without DIG versus reduced CSM referral letter with and without DIG (Arm 1, 2 vs Arm 3, 4).

The sample size was calculated with the following assumptions for the overall effect of the intervention letter: 19% utilization rate for standard letter (Nelson et al. 2012), 37% rate for CSM referral letter alone (based on Medicaid utilization among children: GAO-08-1121, 2008), 57% rate for CSM referral letter + DIG (based on 57% who reported that they took their child to the dentist or had an appointment after receiving the CSM referral letter + DIG in the R34 study). Then, using a two-sided test for equal proportions (namely, a Z test with pooled variance), we find that a sample size of 102 per intervention group per site (thus, 306 subjects per site) will provide 80% power to detect rate differences of 19% versus 37% (as expected for Arm 5 vs Arm 1) or 37% versus 57% (as expected for Arm 1 vs Arm 2) for each site, and 98% power for each of these comparisons using the

combined sample. As siblings (with the same caregiver) may be included in the study, a conservative approach will be to consider the required sample sizes as referring to the number of caregivers. Somewhat greater power will be expected if within-caregiver correlation is less than 1.

For the Ohio site with a total of 889 potential children, we expect 86% to participate (Nelson & Milgrom 2012), with 56% receiving a referral and 5% excluded for emergent needs. From previous [name] study in ECCSD elementary schools we expect 10% of caregivers to have multiple (usually two) children. Thus, an estimated total of 366 caregivers will be available for randomization to the five groups. For the Washington sites, with a total of 1704 potential children, we expect 85% participation (based on 2013 screenings in both districts), with 28% receiving a referral, 5% exclusions for emergent needs, and a 10% reduction in the corresponding number of caregivers due to inclusion of siblings. A total of 347 caregivers will be available for randomization. Even with 5% out of school transfers, the available sample will be adequate for testing the proposed hypothesis. Thus, we expect to randomize 330 caregivers/site to the five study arms to account for any drop-outs at randomization and maintain the required power for the trial.

With regard to our secondary endpoint, the overall IPQ-RD score, we note that our expected sample size will provide for each site 80% power to detect an 10 point decrease in the mean score (e.g., from an expected mean of 127 for the standard letter to 117 for the CSM referral letter) assuming a common standard deviation of 27 (estimated from previous data). A decrease in IPQ-RD scores indicates better illness representation/perception of caregiver. Since the IPQ-RD has never been utilized previously, we refer to a popular rule of thumb (Cohen, 1988) which considers the above standardized effect size of 0.37 (10/27) as a medium, and thus plausible, effect size.

The statistical test of the effect of the targeted component (timeline) will involve a comparison of 408 (Arm 1, 2) versus 48 (Arm 3, 4) subjects. This test may have low power, particularly if the effect of the targeted text is not large. However, including these arms will allow this effect to be estimated and thus provide some idea of its relative contribution in this exploratory analysis, as well as allow us to detect a large effect (if the component is responsible for a large proportion of the CSM referral letter effect).

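### Section 12.2 claims 80% per-site power for a 10-point IPQ-RD difference; the planned 102 caregivers per main arm give about 75%

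*Combined protocol and SAP*

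**What the plan says.** Section 12.2 states that "our expected sample size will provide for each site 80% power to detect an 10 point decrease in the mean score". The example is a two-arm contrast, "from an expected mean of 127 for the standard letter to 117 for the CSM referral letter". The standard deviation is put at 27 in both arms, on the strength of earlier data. No test, alpha, sidedness or number per arm is attached to the 80%.

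The same section gives the sample size for the primary outcome: "a sample size of 102 per intervention group per site", obtained "using a two-sided test for equal proportions (namely, a Z test with pooled variance"). It then says "we expect to randomize 330 caregivers/site to the five study arms". The allocation ratio in Section 5.4.1 is 17:17:2:2:17. The pools are given as "an estimated total of 366 caregivers will be available for randomization to the five groups" (Ohio) and "A total of 347 caregivers will be available for randomization" (Washington), and 5% out-of-school transfers are allowed for.

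For the questionnaire scores, Section 12.4 (Analysis of Secondary Outcomes) plans an F-test across three intervention groups, nominal 95% confidence intervals for pairwise differences, and analyses by site and overall. Its linear model takes the mean response as the dependent variable and adjusts for selected baseline covariates that it does not list. Section 3.2.2 defines the outcome as a change between baseline, two weeks and final follow-up.

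**The concern.** The 80% appears without the inputs needed to check it. When the plan's own arm size is used for the contrast the sentence describes, the result is lower. By-site questionnaire analyses are planned, so this figure will shape how a null result at one site is read. A reader would take the chance of missing a true 10-point difference to be 20%, when it is nearer 25%.

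A smaller gap lies beside it. Sections 3.2.2 and 12.4 do not clearly describe the same analysis, because the supplied text does not say whether the baseline IPQ-RD score enters the model.

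**Working it through.** **Inputs.** Difference 127 − 117 = 10 and SD 27 (Section 12.2). Per main arm per site: 330 × 17/55 = 102, which agrees with the 102 in Section 12.2 and with 204 per main arm over two sites. Two-sided testing and alpha 0.05 are stated for the primary tests only. For the IPQ-RD they are inferred from those tests and from the 95% intervals in Section 12.4.

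**Control: the primary outcome.** A pooled-variance Z test, two-sided 0.05, gives:

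| Comparison | 102 per arm | 204 per arm |
|---|---|---|
| 19% vs 37% | 82.2% | 98.4% |
| 37% vs 57% | 82.1% | 98.3% |

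The stated 80% and 98% are supported, so 102 per arm is the plan's working number.

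**IPQ-RD, two arms, two-sided 0.05.**

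- SE = 27 × √(2/102) = 3.781
- 10/3.781 = 2.645
- Power = Φ(2.645 − 1.960) = 75.3% (noncentral t: 74.9%)

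The stated 80% is not reproduced.

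**What 80% would need.**

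- n = 2 × (1.960 + 0.842)² × 27²/10² = 114.4, so 115 per arm (z) or 116 (t).
- Per site in this ratio: 115 × 55/17 = 372.1, so 373; or 116 × 55/17 = 375.3, so 376. Both exceed the 330 planned and the pools of 366 and 347.
- At 102 per arm: a difference of 2.802 × 3.781 = 10.6 points, or an SD of about 25.5.

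**Other readings of the two-arm test (10 points, SD 27).**

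| Reading | n per arm | z | t |
|---|---|---|---|
| As planned, two-sided | 102 | 75.3% | 74.9% |
| After 5% transfers (102 × 0.95) | 97 | 73.2% | 72.8% |
| Whole Ohio pool (366 × 17/55) | 113 | 79.5% | 79.2% |
| Whole Washington pool (347 × 17/55) | 107 | 77.3% | 76.9% |
| One-sided 0.05 | 102 | 84.1% | 83.9% |
| Both sites combined | 204 | 96.3% | 96.2% |

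**Three-group F-test, alpha 0.05, Arm 5 mean 127, Arm 1 mean 117, SD 27.** The noncentrality is n × Σ(mean − grand mean)²/27².

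| Arm 2 mean | 102 per arm | 97 per arm |
|---|---|---|
| 117 | 78.2% | 76.0% |
| 116.5 | 80.4% | 78.2% |
| 122 | 65.1% | 62.7% |

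The F-test reaches 80% only if the Arm 2 mean is about 116.6 or lower (102 per arm) or about 116.1 or lower (97 per arm). Section 12.2 gives no Arm 2 mean.

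**Precision within one site.** The expected 95% half-width for a pairwise difference is t(0.975, 202) × 3.781 = 7.45, about 7.5 points.

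**The case against.** The strongest reply is that Section 12.4 names a three-group F-test, and the 75% is for a different test. With both CSM arms at 117 the F-test has 78.2%, and an Arm 2 mean only about 0.4 points lower brings it to 80%. A lower Arm 2 mean is plausible, since the information guide is meant to reinforce illness perception; a mean of 116 would give about 82.5%. If the expected sample size meant the whole pools, the F-test at 127/117/117 would have 82.5% (113 per arm) and 80.3% (107 per arm). These calculations are correct, so 80% is not unattainable under every reading. But each route needs an Arm 2 mean the plan does not give, or the randomization of pools larger than the 330 it plans. The example in Section 12.2 is itself a two-arm contrast.

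Section 5.3 also reports lower than expected enrollment and a second recruitment year in Ohio only, with 258 caregivers still needed. Against 660, that implies about 402 already randomized, with no split by site. The even 330/330 division may therefore not hold. This stands as a reason to make any restated power conditional on 102 per arm; it does not support the 80%.

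On the covariate, the separate SAP listed under Supplemental Materials may already name it. With a transformed or rank-based outcome, which Section 12.4 permits, follow-up and change need not give the same contrast. Both limits are accepted.

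**Conclusion.** The concern holds. At the planned 102 per main arm, per-site power for a 10-point IPQ-RD difference is about 75% for a two-sided 0.05 comparison of two arms, or 73% after 5% transfers, against the 80% stated. The F-test comes closer, at 78%, when both CSM arms have mean 117. These figures rest on SD 27, equal arms, the inferred two-sided 0.05 level and no questionnaire non-response beyond that shown; more non-response would lower them.

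The consequence is modest. Only the per-site claim for one secondary endpoint is affected. The primary-outcome figures check out, and combined-site power is about 96%. The baseline-score point is only a gap in Section 12.4 as supplied.

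**What to change.** 1. Restate the Section 12.2 sentence along these lines: with 102 caregivers per main arm per site and SD 27, a two-sided 0.05 comparison of two arms has about 75% power per site for a 10-point difference (80% for about 10.6 points), and about 96% with both sites combined. State the test, alpha, sidedness and n, and say that the figures assume full retention; about 73% applies per site after 5% transfers.
2. If the 80% was meant for the three-group F-test, say so and give the Arm 2 mean assumed.
3. In Section 12.4, name the caregiver's own baseline IPQ-RD score (overall, or for the construct analysed) as a covariate in the 2-week and final follow-up models, or cite where the separate SAP does so. In an untransformed linear model with baseline included, the arm contrast is the same for follow-up score and for change, which reconciles Sections 3.2.2 and 12.4. Claim no power gain unless a baseline-to-follow-up correlation is documented.

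The cost is one restated sentence and one named covariate that is already collected. No data, visits or sample size change, but the stated per-site power becomes less favourable.

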12.3 Planned Interim Analysis

No interim analysis is planned.

12.4 Final Analysis Plan

Primary Statistical Analysis: Descriptive statistics will include frequencies (categorical variables) and means (continuous variables) of baseline covariates among the five intervention groups. Chi-square tests (for categorical variables) and t-tests (for continuous variables) will be performed to test for group differences (by site and overall). In our primary analysis, we will fit multivariate generalized linear (specifically, logistic regression) models with dental care receipt as the (binary) outcome and the child as the unit of analysis (as receipt of dental care will be determined for each child). A generalized estimating equations (GEE) approach (with an exchangeable working correlation structure) will be used to allow for correlations among multiple children for a given caregiver. Separate models will be fit for each site as well as overall. The models will include two indicator variables representing the three interventions. Each model will include an a priori selected set of

baseline variables (listed below) and, for the overall model, an indicator variable for site. Secondarily, we will fit a model with a site by intervention group interaction, and the latter will be tested to formally assess possible intervention effect heterogeneity over sites.

We will also consider working correlation structures (e.g., alternating logistic regressions) that allow for second-level clusters, namely schools (within which the first-level cluster, caregiver, is nested). We will determine final models based on the quasi-likelihood information criterion (QIC). Intervention (and other covariate) effects will be tested using generalized score statistics.

Given the parameter estimates from the above models, we use a model-based standardization approach (Albert et al. 2011) to estimate relative risks (i.e., the ratio of the probabilities of dental usage for a given pair of interventions). A bootstrap approach will be used to obtain a 95% confidence interval for each relative risk. Significance will be determined using a gatekeeper approach to hypothesis testing. Specifically, we will first test for a difference in dental care receipt rates for S vs CSM+DIG (at the 0.05 nominal alpha level). If (and only if) this test is significant, we will proceed to test S vs. CSM alone and CSM vs CSM+DIG (both at the 0.05 nominal alpha level). We will use a similar approach for testing for each site. We will start by testing (for a given treatment comparison) an overall effect (stratifying over sites) at the 0.05 nominal alpha level. If (and only if) this is significant, we will then test (for the same treatment comparison) the effect within each site (at the 0.05 nominal alpha level). A 0.05 family-wise error level is attained in this approach assuming that a (true) effect for S vs. CSM+DIG implies a (true) effect for either S vs. CSM or CSM vs. CSM+DIG (or both), and that an overall effect implies an effect in one or both sites (which is logically the case).

To test the effect of the targeted component (timeline), we will fit the same multivariate generalized linear (specifically, logistic regression) models mentioned above with additional indicator representing reduced text.

Adjustment for Baseline Characteristics: Estimated intervention effects (described above) will be adjusted for the following baseline socio-demographic variables: child's age, race, and caregiver SES, education, and marital status.

Model Assumptions: We will assume that the probabilities of dental care receipt follow the selected logistic regression model (controlling for covariates) mentioned above. We assume that the outcomes for different caregivers (or different schools if a correlation structure for two cluster levels is used) are independent.

Analysis of Secondary Outcomes (Questionnaire data): Summary statistics (including means and standard errors) for questionnaire responses for both the IPQ-RD and behavioral intention items within the caregiver questionnaire will be calculated by site and intervention group. This will be done for the overall questionnaire (IPQ-RD and behavioral intention), for each of the five IPQ-RD cognitive constructs, and the two behavioral intention questions. Analyses will be done by site and overall (controlling for site). A summary measure approach, based on the mean questionnaire response, will be used to compare questionnaire outcomes across intervention groups, for the overall questionnaire and by construct. Specifically, for each construct (or overall) a linear regression model will be used with the mean response as the dependent variable, and intervention group

indicators and selected baseline (control) covariates as independent variables. Inferences (that is, p-values and confidence intervals) will be performed assuming summary measures are normally distributed. This assumption will be tested using the Shapiro-Wilk statistic and if violated a suitable transformation of the summary measure used or a nonparametric approach (e.g., using ranks of the summary measures) conducted.

In the event of missing questionnaire responses, we will first assess whether the data are missing completely at random (MCAR), that is, whether missingness for a given item is dependent only on participant baseline characteristics and not further on any other item responses. This will be done using a generalized estimating equations (GEE) approach, that is, by fitting a multivariate generalized linear (e.g., logistic regression) model to missing data indicators for each item, including as explanatory variables selected baseline covariates and other item responses, and testing for an effect of the latter.

If the MCAR assumption is deemed reasonable (no significant effect found), we will conduct the above regression analyses with mean outcomes based on available data. A weighted analysis (that is, regression with the use of the weighted least squares criterion) will be conducted to adjust for differential missingness (thus, non-homogeneous summary measure variances) among participants. If the MCAR assumption is found to be violated we will use a multiple imputation approach (in conjunction with the summary measure approach) using a suitable imputation model (i.e., using other item responses). For each construct (or overall) we will perform an F-test for a difference in the mean summary measure among the three intervention groups, and obtain nominal 95% confidence intervals for pairwise mean differences. If necessary, we will include a random effect for school.

In addition to assessing the overall effects of the interventions, we will investigate the mechanisms (or paths) through which interventions impact dental care receipt. As represented in Figure 1, we hypothesize that a significant portion of the intervention effect will occur via a three-link path: intervention will affect caregiver illness representation which will in turn affect behavioral intention which will in turn affect dental care receipt. Initially, we will consider an overall average score for caregiver illness representation and for behavioral intention. We have previously developed a generalized causal mediation analysis methodology (Albert and Nelson, 2011) which we can use to estimate and test this specific path effect. It is possible that other paths may also be involved – namely, a direct path (possibly involving unidentified mediators) from intervention to dental care receipt, and paths through either caregiver illness representation or behavioral intention alone. We will therefore decompose the overall effect, and estimate the contribution of each of the four possible paths. For each (broadly defined) mediator, we may be interested in examining multiple components (e.g., summary scores or factors representing specific constructs for caregiver illness representation, and the two questions of behavioral intention). We may thus handle each mediator in our model as multidimensional (that is, a vector of latent or observed variables). In addition, we will consider a further refinement of the model, and decomposition of the intervention effect, by allowing separate paths through the individual components of each mediator. The 2-week measurement time for the mediators reflects the hypothesized time of maximum impact of the intervention. However, we will make use of the 7-month measurements of the mediators to assess any changes in the effect of the intervention over time, as well as the relationship between the mediators (at alternative times) and dental care receipt.

As a supplementary analysis, we will use measurements of self-efficacy (from the Caregiver Questionnaire given at 2 weeks and exit) to test the Health Belief Model as an alternative explanation for the effectiveness of the experimental intervention. Specifically, the mediation effect through self-efficacy will be assessed using a similar model and approach as described above. The relative contribution of the multiple hypothesized mediators will also be examined by including them together in a multiple mediator model.

